13.1.3. Primary Analysis Set

The primary analysis set will include all subjects in the full analysis set who were biomarker positive.

13.1.4. Dose-Limiting Toxicity Evaluable Set

The DLT-evaluable set will include all subjects enrolled in the Dose Escalation part who had a DLT within the first 4 weeks (28 days) on study, or without DLT but received at least 75% of scheduled KRT-232 (AMG 232) doses during the first 3 weeks (21 days). Subjects who complete C1 but are removed from study due to a *TP53* mutation and/or deletion are still eligible to be included in the DLT-evaluable set.

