5.2. KRT-232 (AMG 232) Administration

KRT-232 (AMG 232) will be administered QD for 7 days every 28 days (i.e., 7 consecutive days of dosing followed by 21 consecutive days off treatment).

For QD dosing, subjects should self-administer KRT-232 (AMG 232) with or without food, with a full glass of water. KRT-232 (AMG 232) should not be crushed, chewed, or dissolved in water. Subjects should not be re-dosed with KRT-232 (AMG 232) after vomited doses.

The subject will be requested to maintain a medication diary of each dose of medication. The medication diary will be returned to clinic staff at the end of each course (APPENDIX E).

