5.4. KRT-232 (AMG 232) + Carfilzomib, Lenalidomide, and Dexamethasone Treatment Plan

Dose Regimen

KRT-232 (AMG 232) + carfilzomib, lenalidomide, and dexamethasone will be administered per the following schedule:

Cycles 1-12 (28 day cycle)

- KRT-232 (AMG 232) once daily by mouth 7 out of 28 days
- Carfilzomib 20 mg/m² IV on Days 1 and 2 of Cycle 1, escalating to 27 mg/m² IV on Days 8, 9, 15, 16 of Cycle 1 and continuing on Days 1, 2, 8, 9, 15, 16 of Cycles 2 through Cycle 12
- Lenalidomide 25 mg PO on Days 1-21
- Dexamethasone 40 mg PO or IV on Days 1, 8, 15, and 22

Cycles 13-18 (28 days each)

- KRT-232 (AMG 232) once daily by mouth 7 out of 28 days
- Carfilzomib 27 mg/m² IV on Days 1, 2, 15, and 16
- Lenalidomide 25 mg PO on Days 1-21
- Dexamethasone 40 mg PO or IV on Days 1, 8, 15, and 22

Cycles 19+ (28 days each)

- KRT-232 (AMG 232) once daily by mouth 7 out of 28 days
- Lenalidomide 25 mg PO on Days 1-21
- Dexamethasone 40 mg PO or IV on Days 1, 8, 15, and 22

Part A (Dose-escalation scheme)

The MTD is defined as the highest dose at which six subjects have been treated and less than two subjects experienced DLT within the first cycle of treatment in Phase I of the trial. To determine the MTD, escalation for KRT-232 (AMG 232) will be conducted following the “3+3” design with de-escalation. A cohort of three subjects will be treated at the starting dose level and observed until the end of the first cycle (subjects non-evaluable for DLT will be replaced). The dose level will be escalated with each new cohort until at least one out of three subjects of a cohort experiences DLT. If one subject experiences a DLT, then three additional subjects will be treated at the same dose level; if none of the three additional subjects experiences a DLT, then the dose escalation will be continued by treating the next cohort of three subjects at the next higher dose level. If at least two out of up to six subjects at a dose level experience a DLT, the MTD will be considered to have been exceeded, and up to 3 more subjects will be treated at the next lower dose if there are less than 6 subjects already treated at that dose. The dose steps for escalation are displayed below:

Dose Escalation Schedule	
Dose Level	Dose of KRT-232 (AMG 232)*
- 1	30 mg/day PO x 7 days out of 28 day cycle
+ 1	60 mg/day PO x 7 days out of 28 day cycle
+ 2	90 mg/day PO x 7 days out of 28 day cycle
+ 3	120 mg/day PO x 7 days out of 28 day cycle

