5.6. Definition of Dose-Limiting Toxicity

A DLT is defined as any treatment emergent adverse event (TEAE) during the first treatment cycle that does not have a clear alternative cause (e.g., disease under study, concomitant therapy) based on the following criteria using NCI-CTCAE v5.0:

- Hematological toxicity
 - Grade 3 or 4 neutropenia with fever $\geq 38^0$ C lasting > 48 hours
 - Grade 4 neutropenia lasting > 7 days
 - Grade 3 or 4 thrombocytopenia associated with $>$ grade 1 bleeding. Grade 4 thrombocytopenia that persists for > 14 days, despite holding treatment
 - Grade 4 anemia, unexplained by underlying disease
 - Any other grade 4 hematologic toxicity that does not resolve to subject's pre-treatment baseline level within 72 hours
- Non-hematological toxicity
 - Grade ≥ 3 nausea, vomiting or diarrhea lasting longer than 72 hours despite optimal medical support
 - Grade ≥ 3 non-hematological toxicity (excluding increased serum creatinine, or electrolyte abnormalities that are not clinically significant and require no treatment)
 - Any grade 3 electrolyte abnormalities that do not resolve to grade ≤ 2 within 72 hours
 - Grade 3 fatigue persisting > 7 days
 - Grade ≥ 3 acute kidney injury (creatinine $> 3 \times$ baseline or > 4.0 mg/dL) lasting > 72 hours
 - Any other grade 3 or 4 non-hematologic toxicities not predefined above will be considered a DLT.
 - A delay of ≥ 14 days in commencing Cycle 2 Day 1 due to lack of adequate

recovery of KRT-232 (AMG 232) +KRD-related toxicities will be considered a DLT.

Subjects who receive < 75% of the planned study drug doses during the first cycle of (i.e. $\leq 5/7$ daily doses of KRT-232 (AMG 232) will be considered non-evaluable for purposes of determining the MTD (unless due to a DLT) and will be replaced. Subjects who experience a DLT during the DLT-evaluable period will be considered evaluable for the purposes of determining the MTD as per Section 13.1.4

Management and dose modifications associated with the above adverse events are outlined in Section 6.

Dose escalation will proceed within each cohort according to the following scheme. Dose-limiting toxicity (DLT) is defined above.

Number of Subjects with DLT at a Given Dose Level	Escalation Decision Rule
0 out of 3	Enter 3 subjects at the next dose level.

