13.2. Study Design/Endpoints

The primary endpoint is to assess the safety and tolerability of KRT-232 (AMG 232) + KRd in subjects with relapsed and/or refractory myeloma and to determine the MTD/tentative RP2D of KRT-232 (AMG 232) + KRd.

All subjects who receive any amount of the study drug will be evaluable for toxicity. The DLT-evaluable period will be during cycle 1, although toxicity will be monitored throughout the course of treatment. The primary analysis will occur after all subjects in Part B have either discontinued the study or completed at least 6 months of treatment.

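### The DLT-evaluability test can be met by Day 6 and does not require observation through the 28-day DLT window, so a subject lost to observation later in Cycle 1 counts as DLT-free and is not replaced

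*Combined protocol and SAP*

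**What the plan says.** Section 13.1.4 gives two routes into the DLT-evaluable set. One is for a subject who "had a DLT within the first 4 weeks (28 days) on study". The other is for a subject "without DLT but received at least 75% of scheduled KRT-232 (AMG 232) doses during the first 3 weeks (21 days". It adds that a subject who finishes Cycle 1 and is then removed for a *TP53* result can stay in the set.

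Section 5.6 and the synopsis state the rule from the other side. A subject who receives less than 75% "of the planned study drug doses during the first cycle of" treatment, spelled out as five or fewer of the seven KRT-232 doses, "will be considered non-evaluable for purposes of determining the MTD (unless due to a DLT) and will be replaced".

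Other sections bear on the point:

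- Section 5.2 gives the KRT-232 schedule as "7 consecutive days of dosing followed by 21 consecutive days off treatment"; the calendar in 10.1 places the doses on Days 1-7.
- Section 13.2: "The DLT-evaluable period will be during cycle 1".
- Section 5.4 says that a cohort is "observed until the end of the first cycle (subjects non-evaluable for DLT will be replaced", and note a to the 10.1 calendar puts the cohort DLT review after Day 28.
- Section 5.10 follows subjects for 30 days after removal from study, or until death. The synopsis (Study Duration) counts 30 days from the last treatment and stops sooner if the next line of therapy begins.

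**The concern.** The two routes in 13.1.4 use different clocks. A DLT counts over 28 days, but absence of a DLT is accepted on a dose count that can be complete by Day 6. The 21-day clause does not help, because no KRT-232 is scheduled after Day 7. Section 5.4 ties replacement to being non-evaluable, and a subject who took six doses and then disappeared is not non-evaluable under any section. That subject enters the 3+3 count as a non-event.

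Part A's primary objective is the MTD and RP2D in combination with KRd, decided on cohorts of three to six. One subject wrongly scored as DLT-free can change a decision, and always in the direction of escalating or accepting a dose. Once later cohorts have been treated, the decision cannot be taken back.

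**Working it through.** **1. The plan's own equivalence.** Section 5.6 equates less than 75% with five or fewer of seven doses. 5/7 = 71.4% fails and 6/7 = 85.7% passes, so this reproduces. With no missed dose, the test is met on Day 6, leaving 28 − 6 = 22 days of the window.

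**2. What has not yet been seen.** By the end of Day 7, on the 5.4 schedule, a subject has had:

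- 2 of 6 carfilzomib doses: 2×20 = 40 of 2×20 + 4×27 = 148 mg/m², or 27%;
- 7 of 21 lenalidomide doses;
- 1 of 4 dexamethasone treatment doses.

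Some DLT criteria in 5.6 cannot be settled by then, such as grade 4 neutropenia beyond 7 days and grade 4 thrombocytopenia beyond 14 days. The criterion of a delay of at least 14 days in starting Cycle 2 is not settled even at Day 28: Cycle 2 Day 1 is nominally Day 29, and 29 + 14 = Day 43.

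**3. Does another section make an unobserved subject non-evaluable?** Section 5.4 and calendar note a say when cohorts are observed and reviewed. Sections 5.10 and the synopsis say how long subjects are followed. Section 5.6 makes a subject non-evaluable only for too few KRT-232 doses. None makes missing observation a ground for exclusion or replacement.

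**4. One unobserved subject in the first cohort.** Take a true DLT risk p = 0.33, the limit in 2.6. With full observation:

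P(escalate) = (1−p)³ + 3p(1−p)²·(1−p)³ = 0.301 + 0.444×0.301 = 0.434.

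Now let one of the first three be unobserved after about Day 7, with a share f of DLTs falling later (assumed). That subject's observable risk is r = p(1−f), and

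P(escalate) = (1−p)²(1−r) + [r(1−p)² + (1−r)·2p(1−p)]·(1−p)³.

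- f = 0.50, r = 0.165: 0.375 + 0.443×0.301 = 0.508
- f = 0.75, r = 0.0825: 0.412 + 0.443×0.301 = 0.545
- f = 1, r = 0: 0.449 + 0.442×0.301 = 0.582

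**5. Leaving spread over all subjects.** Let a share q of subjects without an early DLT leave at about Day 7 unobserved, and a share g of DLTs fall later. Neither figure is in the documents. Under the current rule the counted DLT rate is p(1−qg). If leavers without a DLT are replaced, it is

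[p(1−g) + (1−q)pg] / [p(1−g) + (1−p(1−g))(1−q)].

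Putting these rates into the full-observation formula of step 4, with p = 0.33 and g = 0.75:

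| q (assumed) | P(pass), current rule | P(pass), leavers replaced |
|---|---|---|
| 0 | 43.4% | 43.4% |
| 5% | 45.9% | 42.9% |
| 10% | 48.4% | 42.3% |
| 20% | 53.5% | 40.9% |

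For example, at q = 10% the current counted rate is 0.33×(1 − 0.075) = 0.305. With replacement it is 0.30525/0.90825 = 0.336.

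**The case against.** A reader might infer that anyone who stops treatment after Day 6 is scored DLT-free. The documents do not support that. A DLT within 28 days counts whether or not treatment continues. Section 5.10 follows a subject removed on Day 8 to about Day 38, past the window, and 13.2.2 collects treatment-emergent events to 30 (±5) days after the last dose. Sections 5.4 and 6 also score a subject who needs a Cycle 1 dose reduction as a DLT. What remains is withdrawal of consent, loss to follow-up and, on the synopsis wording, early start of another therapy.

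The sizes are conditional. No departure rate is stated, and the 58% figure assumes that no DLT would occur in the first week.

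It can also be said that observation to the end of the cycle was presupposed: 5.4 says so for cohorts, and the *TP53* sentence in 13.1.4 speaks of completing Cycle 1. That is probably the intent. But the sentence defining the set does not ask for it, and the *TP53* sentence covers only those removals.

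Part B gives a later check. Section 5.7 calls for discussion of the RP2D if 2 of the first 5 expansion subjects have a DLT. At p = 0.33, P(at least 2 of 5) = 1 − 0.67⁵ − 5×0.33×0.67⁴ = 53%. This tempers the consequence but prompts only a discussion, after the dose has been chosen.

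**Conclusion.** The point holds for subjects lost to observation. As written, 13.1.4 can count a subject who was not observed through the DLT window as a non-DLT, and nothing requires replacement. The direction is toward escalation. At 33% true risk, P(escalate) goes from 43% to 51-58% when one of the first three is unobserved and 50-100% of DLTs are late. Across all subjects it goes from 43.4% to 45.9-48.4% with 5-10% leaving and 75% of DLTs late. These shares are assumptions; with no leavers the effect is zero. The reading of the text is firm, and the size is not.

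A reader might go further and infer that the rule is invalid without a minimum exposure to carfilzomib, lenalidomide and dexamethasone, or that the MTD of the four-drug regimen will be set too high. The documents do not support either. Only KRT-232 is escalated, and 2.6 describes KRd at these doses as having an acceptable, well-studied safety profile, so testing exposure to KRT-232 alone is a defensible design choice. The narrower gap is that no evaluability text says how omitted KRd doses are treated, for example lenalidomide held for neutropenia under 6.4 and resumed at the same level.

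**What to change.** In 13.1.4, 5.6 and the synopsis, use one definition: a subject without a DLT is evaluable only if the 75% KRT-232 test is met **and** DLT assessment was completed through the DLT window; otherwise the subject is replaced. In addition:

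- delete the 21-day clause from 13.1.4;
- reconcile the 28-day window with the Cycle 2 delay criterion in 5.6, which cannot be judged by Day 28;
- reconcile the follow-up wording in 5.10 with that in the synopsis;
- keep the *TP53* clause;
- state whether omitted KRd doses affect evaluability, with any threshold left to the sponsor.

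The cost is amendment wording and an occasional extra replacement subject in Part A, where non-evaluable subjects are already replaced. Replacement also brings a slight conservative bias, because leavers with a DLT are kept and those without are not. In the model above, the pass probability falls from 43.4% to 42.9% at 5% leaving and to 42.3% at 10%.

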13.1.5. Safety Analysis Set

The safety analysis set will include all subjects enrolled who received any amount of KRT-232 (AMG 232). Subjects will be summarized according to treatment actually received.

Three groups of subjects will be identified within the safety analysis set: (1) subjects in the Dose Escalation part, (2) subjects in the Dose Expansion part, and (3) all subjects in the study.

13.1.6. Pharmacokinetic Analysis Set

The PK analysis set will include all subjects in the enrolled analysis set who received any amount of KRT-232 (AMG 232) and had measurable plasma concentrations of KRT-232 (AMG 232).

13.1.7. Pharmacodynamic/Biomarker Analysis Set

The biomarker analysis set will include all subjects in the enrolled analysis set who received any amount of KRT-232 (AMG 232) and who had the baseline assessment and where applicable, at least 1 post-baseline assessment for biomarkers.

13.2. Study Design/Endpoints

The primary endpoint is to assess the safety and tolerability of KRT-232 (AMG 232) + KRd in subjects with relapsed and/or refractory myeloma and to determine the MTD/tentative RP2D of KRT-232 (AMG 232) + KRd.

All subjects who receive any amount of the study drug will be evaluable for toxicity. The DLT-evaluable period will be during cycle 1, although toxicity will be monitored throughout the course of treatment. The primary analysis will occur after all subjects in Part B have either discontinued the study or completed at least 6 months of treatment.

13.2.1. Safety Analyses

Safety parameters will include SAEs, TEAEs, physical examination findings (including ECOG performance status), vital sign measurements, and standard clinical laboratory parameters (serum chemistry, hematology, urinalysis). Adverse events will be graded according to the NCI-CTCAE v5.0. In the Dose Escalation part, the incidence of DLTs will also be evaluated.

Safety analyses in general will be descriptive and will be presented in tabular format with the appropriate summary statistics. In the Dose Escalation part, the number of DLTs identified among the DLT-evaluable subjects in the DLT-evaluable set will be listed and summarized for each dose of KRT-232 (AMG 232).

13.2.2. Adverse Event Analyses

A TEAE is defined as an adverse event that emerges during the treatment period (from first dose date till 30 (\pm 5) days after the last dosing date), having been absent at pre-treatment; or reemerges during treatment, having been present at baseline but stopped prior to treatment; or worsens in severity after starting treatment relative to the pre-treatment state, when the adverse event is continuous. The number and percentage of subjects reporting TEAEs will be tabulated by the worst NCI- CTCAE grade, system organ class (SOC), and preferred term.

Similarly, the number and percentage of subjects reporting treatment-emergent SAEs will be tabulated, as well as TEAEs/SAEs considered related to KRT-232 (AMG 232) + KRd.

A by-subject adverse event (including TEAE) data listing will be provided including, but not limited to, verbatim term, preferred term, SOC, NCI-CTCAE grade, and relationship to study drug.

Deaths, other SAEs, and other significant adverse events, including those leading to permanent discontinuation from KRT-232 (AMG 232) + KRd, will be listed.

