Study Duration:	Subjects will receive KRT-232 (AMG 232) + KRD at a dose defined by the treatment outline above. This therapy will be continued without a cap on the number of allowed cycles, unless one of the following occurs: 
• Disease progression by IMWG criteria (Appendix 15.6).• Unacceptable adverse event(s) defined as:
◦ Occurrence of an AE that is related to treatment with the study drug which, in the judgment of the investigator, compromises the subject's ability to continue study-specific procedures, or is considered to not be in the subject's best interest.◦ Persistent AE requiring a delay of therapy for more than 4 weeks (28 days)• Subject decides to withdraw from the study• Pregnancy
◦ All women of child bearing potential should be instructed to contact

	
the investigator immediately if they suspect they might be pregnant (e.g., missed or late menstrual period) at any time during study participation.
 
○ The investigator must immediately notify CTEP in the event of a confirmed pregnancy in a subject participating in the study.● Termination of the study by sponsor● The drug manufacturer can no longer provide the study agent● Subject achieves complete remission (CR), and the subject and investigator feel that discontinuation of KRT-232 (AMG 232) + KRd is in the subject's best interests, or● Subject achieves a level of response that qualifies him or her for another therapy, such as high dose therapy with autologous stem cell transplantation, and the subject and investigator feel that discontinuation of KRT-232 (AMG 232) + KRd is in the subject's best interests 
At the completion or early discontinuation of treatment, subjects will be followed for an additional 30 days after the last administration of treatment or up until the initiation of the next line of treatment, whichever comes first. Subjects with adverse events until the event has resolved or the condition has stabilized.

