2.4.3. Carfilzomib, Lenalidomide, and Dexamethasone (KRd)

The combination of carfilzomib, lenalidomide, and dexamethasone (KRd) was studied in a phase 1 trial in relapsed and refractory myeloma (Niesvizky et al., 2013), where the MTD was not reached and the maximum planned dose (Dose Level 6) of KRd (Carfilzomib 27 mg/m²,

lenalidomide 25 mg, and dexamethasone 40 mg) was recommended for further study.. Based on the encouraging results of the safety, tolerability, and efficacy of this study and a subsequent phase 2 study (Wang et al., 2013), the combination of carfilzomib, lenalidomide, and low-dose dexamethasone (KRd) was then compared to lenalidomide and low-dexamethasone (Rd) in a phase 3 registration-enabling randomized study in relapsed myeloma patients with 1-3 lines of prior therapy (ASPIRE) (Stewart, 2015). In this study, KRd was administered per the following schedule:

Cycles 1-12 (28 day cycle)
Carfilzomib 20 mg/m ² IV on Days 1 and 2 of Cycle 1, escalating to 27 mg/m ² IV on Days 8, 9, 15, 16 of Cycle 1 and continuing on Days 1, 2, 8, 9, 15, 16 of Cycles 2 through Cycle 12
Lenalidomide 25 mg PO on Days 1-21
Dexamethasone 40 mg PO or IV on Days 1, 8, 15, and 22
Cycles 13-18 (28-day cycle)
Carfilzomib 27 mg/m ² IV on Days 1, 2, 15, and 16
Lenalidomide 25 mg PO on Days 1-21
Dexamethasone 40 mg PO or IV on Days 1, 8, 15, and 22
Cycles 19+ (28-day cycle)
Lenalidomide 25 mg PO on Days 1-21
Dexamethasone 40 mg PO or IV on Days 1, 8, 15, and 22

Both ORR (87.1% vs. 66.7%) and PFS (26.3 vs. 17.6 months) were superior in the KRd arm compared to the Rd arm. Most common grade 3 or 4 AEs in the KRd arm were anemia (17.9%) neutropenia (29.6%) and thrombocytopenia (16.6%). Non-hematologic grade 3 or 4 AEs occurring in \geq 5% of subjects included fatigue (7.7%) and hypokalemia (9.4%). Based on the positive results of this study, KRd was granted FDA approval in 2015 for subjects with relapsed myeloma with 1-3 lines of therapy, and established itself as a standard-of-care in this patient population.

2.5. Rationale of KRT-232 (AMG 232) + Carfilzomib, Lenalidomide, and Dexamethasone (KRd) in Multiple Myeloma

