INJURY, POISONING AND PROCEDURAL COMPLICATIONS - Fracture; Hip fracture; Vascular access complication

INVESTIGATIONS - Activated partial thromboplastin time prolonged; Cholesterol high; Creatinine increased; Electrocardiogram QT corrected interval prolonged; INR increased; Investigations - Other (hemochromatosis)

METABOLISM AND NUTRITION DISORDERS - Acidosis; Hypercalcemia; Hyperkalemia; Hypoglycemia

MUSCULOSKELETAL AND CONNECTIVE TISSUE DISORDERS - Arthritis; Chest wall pain; Joint effusion; Muscle weakness lower limb; Neck pain; Osteonecrosis of jaw¹²

NEOPLASMS BENIGN, MALIGNANT AND UNSPECIFIED (INCL CYSTS AND POLYPS) - Tumor pain

NERVOUS SYSTEM DISORDERS - Ataxia; Cognitive disturbance; Dysphasia; Edema cerebral; Encephalopathy; Intracranial hemorrhage; Ischemia cerebrovascular; Leukoencephalopathy; Memory impairment; Nervous system disorders - Other (hyporeflexia); Spinal cord compression; Seizure; Somnolence; Transient ischemic attacks

PSYCHIATRIC DISORDERS - Agitation; Anxiety; Confusion; Psychosis

RENAL AND URINARY DISORDERS - Urinary frequency; Urinary incontinence; Urinary tract pain

REPRODUCTIVE SYSTEM AND BREAST DISORDERS - Reproductive system and breast disorders - Other (hypogonadism); Vaginal hemorrhage

RESPIRATORY, THORACIC AND MEDIASTINAL DISORDERS - Adult respiratory distress syndrome; Allergic rhinitis; Atelectasis; Bronchopulmonary hemorrhage; Hypoxia; Laryngeal mucositis; Pharyngeal mucositis; Pleural effusion; Pulmonary hypertension; Respiratory failure; Tracheal mucositis; Voice alteration

SKIN AND SUBCUTANEOUS TISSUE DISORDERS - Alopecia; Nail loss; Photosensitivity; Rash acneiform; Skin and subcutaneous tissue disorders - Other (Sweet's Syndrome); Urticaria

VASCULAR DISORDERS - Hot flashes; Phlebitis; Vascular disorders - Other (hemorrhage NOS)

Note: Lenalidomide (CC-5013) in combination with other agents could cause an exacerbation of any adverse event currently known to be caused by the other agent, or the combination may result in events never previously associated with either agent.

Adverse Event List(s) for other Commercial Agent(s)

In the Phase 3 randomized ASPIRE (Stewart et al., 2015) trial of carfilzomib, lenalidomide, and dexamethasone (KRd) vs. lenalidomide and dexamethasone (Rd), the following adverse reactions occurred in $\geq 10\%$ of subjects in the KRd arm during cycles 1-12.

	KRd Arm (N = 392) n (%)	
Adverse Reactions by Body System	Any Grade	\geq Grade 3
Blood and Lymphatic System Disorders		

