13.2.3. Clinical Laboratory Evaluation Analyses

Descriptive statistics will be provided for selected clinical laboratory test results (hematology and blood chemistry) and changes from baseline by scheduled time of evaluation, including the End-of-Treatment Visit, maximum post-treatment value, and minimum post-treatment value.

Abnormal laboratory results will be graded according to NCI-CTCAE, v5.0, if applicable. A shift table, presenting the 2-way frequency tabulation for baseline and the worst post-treatment value according to the NCI-CTCAE grade, will be provided for selected clinical laboratory tests.

Abnormal clinical laboratory test results that are deemed of clinical significance or of grade 3 or 4 will be listed.

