13.5. Analysis of Secondary Endpoints

PK and PD analysis

Descriptive statistics will be provided for selected PK, and PD data by dose and time as appropriate. Descriptive statistics on continuous data will include means, medians, standard deviations, and ranges, while categorical data will be summarized using frequency counts and percentages. Graphical summaries of the data may be presented.

A full pharmacokinetic profile of KRT-232 (AMG 232) will be proposed in this protocol to assess exposure-response relationships with various PD endpoints (i.e., MIC-1 changes, toxicity, efficacy). KRT-232 (AMG 232) concentrations in these samples will be quantitatively measured using liquid chromatography/tandem mass spectrometric (LC/MS/MS) method that will be developed by the Analytical Pharmacology Core Laboratory at the Sidney Kimmel Comprehensive Cancer Center (SKCCC) at Johns Hopkins. For KRT-232 (AMG 232), the individual PK parameters from a single dose will be estimated for C_{max} , AUC, $T_{1/2}$, apparent Cl/F, and apparent V/F using non-compartmental or compartmental PK methods with the software WinNonlin. For serum MIC-1 levels, each individual level will be normalized to the baseline level for that subject. Advanced population PK methods may be employed to assess the link between drug exposure and biological effects and efficacy. The PK variables and changes in MIC-1 will be tabulated and descriptive statistics (e.g., geometric means and coefficients of variation) calculated for each dose level. PK parameters (i.e., $T_{1/2}$, Cl, and AUC) and MIC-1 changes will be compared across dose level using nonparametric statistical testing techniques. Exploratory correlative studies with pharmacodynamic (biological endpoints, toxicity and efficacy) will be analyzed using nonparametric statistics. Significance for comparisons will be at the $p<0.05$ level.

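### Whole-treatment TEAE percentages and worst values, compared by dose or study part, are confounded with length of follow-up, because earlier cohorts are observed longer than Part B

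*Combined protocol and SAP*

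**What the plan says.** Section 13.2.2 counts TEAEs from first dose to 30 (±5) days after last dose and summarises them crudely: "The number and percentage of subjects reporting TEAEs will be tabulated by the worst" CTCAE grade, system organ class and preferred term. Section 13.2.3 adds shift tables using "the worst post-treatment value according to the NCI-CTCAE grade", and 13.2.3 and 13.2.4 report maximum and minimum post-treatment laboratory and vital-sign values.

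The synopsis (Study Duration) sets no limit on treatment: "This therapy will be continued without a cap on the number of allowed cycles". Sections 5.4 and 5.6 fill dose levels one after another. Section 13.2 fixes the timing: "The primary analysis will occur after all subjects in Part B have either discontinued the study or completed at least 6 months of treatment".

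Safety is to be summarised by dose and time as appropriate (synopsis, Statistical Considerations) and by study part (13.1.5: "Three groups of subjects will be identified within the safety analysis set"). The exposure-response relationship with toxicity is a secondary objective in both parts. Section 13.5 says: "Exploratory correlative studies with pharmacodynamic (biological endpoints, toxicity and efficacy) will be analyzed using nonparametric statistics", with significance at p<0.05. No section defines the toxicity variable for that analysis.

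For TEAEs, Section 13 gives no common window, exposure-adjusted rate or time-to-first-event summary. For efficacy, 13.6 does handle unequal follow-up, with Kaplan-Meier estimates and censoring.

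**The concern.** The length of the TEAE window is tied to dose by design. Level 1 subjects enter first and can be treated longest before the cut; Part B subjects enter last. A crude percentage of subjects ever affected, or a worst value ever recorded, grows with time observed. Placing such columns next to each other by dose or by part compares toxicity and follow-up together.

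Part B exists to confirm tolerability, and the by-dose safety picture will inform how the RP2D is described. If lower-dose subjects collect late events only because they are watched longer, a real rise with dose looks smaller than it is. A Part A cohort treated at the Part B dose would make Part B look safer than it is.

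**Working it through.** **Inputs from the plan.** Five levels of 3 to 6 subjects, plus 10 in Part B, 25 to 40 in total. Accrual is given both as 1.5 and as 2.5 per month (13.3), so both are used. The cut is taken as last enrolment plus 6 months (13.2).

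**Assumptions.** All five levels are used and subjects enter evenly. Time on treatment is exponential. The plan states no median, so 26.3 months (the KRd PFS cited in 2.4.3, an upper case) and 12 and 6 months are tried.

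**Plan's own figure.** 25/1.5 = 16.7 and 40/1.5 = 26.7 months, stated as 16-26. The rate of 2.5 per month would give 10 and 16 months, so the two rates in 13.3 need reconciling.

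**Available follow-up.** Subject i of N has (N − i)/rate + 6 months. At 1.5 per month:
- Level 1, N = 25, mean i = 2: 23/1.5 + 6 = 21.3 months.
- Level 1, N = 40, mean i = 3.5: 36.5/1.5 + 6 = 30.3 months.
- Part B, on average 4.5 places from the end: 4.5/1.5 + 6 = 9.0 months.

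**Expected time on treatment.** (1 − exp(−λF))/λ, with λ = ln 2/median and F the follow-up, averaged over subjects. For a 26.3-month median, λ = 0.0264. Level 1 gives 16.3 months (N = 25) or 20.9 (N = 40); Part B gives 8.0.

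Ratio of mean time on treatment, level 1 to Part B (level 5 to Part B in brackets):

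| Accrual per month | Subjects per level | Median 26.3 | Median 12 | Median 6 |
|---|---|---|---|---|
| 1.5 | 3 | 2.05 (1.41) | 1.76 (1.34) | 1.43 (1.23) |
| 1.5 | 6 | 2.62 (1.50) | 2.06 (1.40) | 1.52 (1.27) |
| 2.5 | 3 | 1.78 (1.29) | 1.62 (1.25) | 1.40 (1.18) |
| 2.5 | 6 | 2.26 (1.36) | 1.92 (1.30) | 1.54 (1.22) |

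If escalation stops after one to three levels, the level 1 ratio is about 1.2 to 2.1. Adding the 30-day tail and a 28-day pause between cohorts raises the top of the five-level range only slightly, to about 2.8.

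**Effect on percentages (illustration).** Assume a constant event hazard h of 0.05 per month while on treatment. The proportion affected is h/(h + λ) × (1 − exp(−(h + λ)F)), averaged over subjects. At 1.5 per month and 3 per level:

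| Median on treatment | True hazard ratio, Part B to level 1 | Whole treatment: level 1 vs Part B | First 6 months: level 1 vs Part B |
|---|---|---|---|
| 26.3 | 1 | 53% vs 32% | 24% vs 24% |
| 26.3 | 2 | 53% vs 53% | 24% vs 42% |
| 26.3 | 3 | 53% vs 67% | 24% vs 56% |
| 6 | 2 | 29% vs 39% | 19% vs 34% |

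For the same dose and no true difference, level 5 against Part B shows 42% vs 32% at a 26.3-month median and 27% vs 23% at 6 months.

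**How late events fall.** Section 7.1 tabulates grade 3 or higher reactions among "subjects in the KRd arm during cycles 1-12" (n = 392); 2.4.3 gives overall grade 3-4 rates. One minus their ratio is the share of affected subjects not seen by cycle 12:
- Neutropenia: 1 − (104/392)/0.296 = 10%.
- Thrombocytopenia: 1 − (58/392)/0.166 = 11%.
- Anemia: 1 − (53/392)/0.179 = 25%.
- Hypokalemia: 1 − (22/392)/0.094 = 40%.

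This assumes that the two sources use comparable definitions and data cuts, which the documents do not show. It suggests only that the size of the bias differs by event.

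**The case against.** Safety analyses are declared generally descriptive, and 13.2.2 itself names no dose contrast. The only by-dose safety summary specified in 13.2 is the DLT count, which uses Cycle 1. This stands in part. No formal TEAE test is at risk, but the synopsis plans safety by dose and 13.1.5 sets up the parts as reporting groups, so readers will compare the columns.

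Laboratory and vital-sign summaries by scheduled time (13.2.3, 13.2.4) are already comparable across cohorts. That stands; only the worst, maximum and minimum values are affected.

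A reader might infer that the exposure-toxicity analysis is biased by design. The documents do not support that. PK is sampled only on Cycle 1 Days 1-2, and the toxicity variable is undefined. If it were Cycle 1 DLT there would be no such bias; if it were a whole-treatment TEAE there would be.

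A reader might also infer that the bias always works against finding a dose effect. It does not. If escalation passes the MTD, a Part A cohort above the RP2D is watched longer than Part B, and the contrast exaggerates the dose effect.

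Finally, with three subjects per level, chance outweighs this bias: 2 of 3 affected has an exact 95% interval of 9% to 99%. That is true of a single level, but it does not excuse a systematic difference in observation time, which also affects pooled Part A against Part B.

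**Conclusion.** The point holds as a confounded descriptive comparison. Crude whole-treatment TEAE percentages and worst, maximum or minimum laboratory and vital-sign values are not comparable across dose levels or study parts. Observation time differs by a factor of about 1.4 to 2.6 for level 1 against Part B and 1.2 to 1.5 for level 5 against Part B. These ranges rest on full five-level escalation, exponential time on treatment with a median of 6 to 26.3 months, and the plan's two accrual rates.

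It would be tempting to say that early cohorts are watched twice as long and that a dose effect is hidden. Both are particular scenarios. A ratio of 2 or more needs the longer medians, mostly with larger cohorts. Complete masking needs a hazard ratio near 2 together with long treatment; at a 6-month median, or with a hazard ratio of 3, the effect is shrunk but visible. The bias is small for events confined to early cycles.

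Cycle 1 DLT counts, the MTD rule and the DLT monitoring in Part B are not affected.

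**What to change.** In 13.2.2 to 13.2.4, state that any comparison of TEAEs, or of worst, maximum or minimum laboratory or vital-sign values, across dose level or study part uses a common window: Cycle 1, and the first 6 cycles. Six 28-day cycles are 168 days, so the window fits within the 6-month Part B cut apart from dosing delays. Handle subjects who stop earlier by cumulative incidence or time to first event.

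In 13.5, define the exposure-toxicity variable as worst grade within that window.

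Keep the whole-treatment tables as description. Show median cycles received and events per patient-month for each column, and say that these percentages are not for comparison between doses or parts.

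The cost is a change of wording in Section 13 and one extra set of tables from data already collected. The downside is that events after cycle 6 do not enter the comparison, though they remain in the descriptive tables.
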